12.2.7. Source Documents

- Source documents provide evidence for the existence of the participant and substantiate the integrity of the data collected. Source documents are filed at the investigator's site.
- Data reported on the CRF or entered in the eCRF that are transcribed from source documents must be consistent with the source documents or the discrepancies must be explained. The investigator may need to request previous medical records or transfer records, depending on the study. Also, current medical records must be available.

12.2.8. Study and Site Closure

GSK or its designee reserves the right to close the study site or terminate the study at any time for any reason at the sole discretion of GSK. Study sites will be closed upon study completion. A study site is considered closed when all required documents and study supplies have been collected and a study-site closure visit has been performed. If GSK determine such action is needed, GSK will discuss the reasons for taking such action with the investigator or the head of the medical institution (where applicable). When feasible, GSK will provide advance notification to the investigator or the head of the medical institution, where applicable, of the impending action

The investigator may initiate study-site closure at any time, provided there is reasonable cause and sufficient notice is given in advance of the intended termination.

Reasons for the early closure of a study site by the sponsor or investigator may include but are not limited to:

- Failure of the investigator to comply with the protocol, the requirements of the IRB/IEC or local health authorities, the sponsor's procedures, or GCP guidelines
- Inadequate recruitment of participants by the investigator
- Discontinuation of further study treatment development

12.2.9. Records Retention

- Following closure of the study, the investigator or the head of the medical institution (where applicable) must maintain all site study records (except for those required by local regulations to be maintained elsewhere), in a safe and secure location.
- The records must be maintained to allow easy and timely retrieval, when needed (e.g., for a GSK audit or regulatory inspection) and must be available for review

in conjunction with assessment of the facility, supporting systems, and relevant site staff.

- Where permitted by local laws/regulations or institutional policy, some or all of these records can be maintained in a format other than hard copy (e.g., microfiche, scanned, electronic); however, caution needs to be exercised before such action is taken.
- The investigator must ensure that all reproductions are legible and are a true and accurate copy of the original and meet accessibility and retrieval standards, including re-generating a hard copy, if required. Furthermore, the investigator must ensure there is an acceptable back-up of these reproductions and that an acceptable quality control process exists for making these reproductions.
- GSK will inform the investigator of the time period for retaining these records to comply with all applicable regulatory requirements. The minimum retention time will meet the strictest standard applicable to that site for the study, as dictated by any institutional requirements or local laws or regulations, GSK standards/procedures, and/or institutional requirements.
- The investigator must notify GSK of any changes in the archival arrangements, including, but not limited to, archival at an off-site facility or transfer of ownership of the records in the event the investigator is no longer associated with the site.

12.2.10. Dissemination of Clinical Study Data

- Study information from this protocol will be posted on publicly available clinical trial registers before enrollment of subjects begins
- Where required by applicable regulatory requirements, an investigator signatory will be identified for the approval of the clinical study report. The investigator will be provided reasonable access to statistical tables, figures, and relevant reports and will have the opportunity to review the complete study results at a GSK site or other mutually-agreeable location.
- All study investigators will be provided with the full summary of the study results. The investigator is encouraged to share the summary results with the study subjects, as appropriate.
- The procedures and timing for public disclosure of the results summary and for development of a manuscript for publication will be in accordance with GSK Policy.

12.2.11. Publication Policy

- The results of this study may be published or presented at scientific meetings. If this is foreseen, the investigator agrees to submit all manuscripts or abstracts to the sponsor before submission. This allows the sponsor to protect proprietary information and to provide comments.
- The sponsor will comply with the requirements for publication of study results. In accordance with standard editorial and ethical practice, the sponsor will

generally support publication of multicenter studies only in their entirety and not as individual site data. In this case, a coordinating investigator will be designated by mutual agreement.

- Authorship will be determined by mutual agreement and in line with International Committee of Medical Journal Editors authorship requirements

12.2.12. Clinical Events Committee

An external independent CEC blinded to treatment allocation will adjudicate all clinical events reported during this study that are referred for adjudication, including major adverse cardiovascular events (MACE; composite of all-cause mortality [CV and non-CV mortality], non-fatal MI and non-fatal stroke) and additional components for a broader definition of MACE including thromboembolic events (vascular access thrombosis, symptomatic deep vein thrombosis, symptomatic pulmonary embolism), and hospitalization for heart failure (Section [9.3.5](#)).

12.2.13. Safety Review Team (SRT)

An internal Safety Review Team, which includes GSK personal involved in the conduct of the study, will review periodically blinded safety data from this trial.

12.3. Appendix 3: Adverse Events: Definitions and Procedures for Recording, Evaluating, Follow-up, and Reporting

Definition of AE

AE Definition

- An AE is any untoward medical occurrence in a clinical study participant, temporally associated with the use of a study treatment, whether or not considered related to the study treatment.
- NOTE: An AE can therefore be any unfavorable and unintended sign (including an abnormal laboratory finding), symptom, or disease (new or exacerbated) temporally associated with the use of a study treatment.

Events Meeting the AE Definition

- Any abnormal laboratory test results (hematology, clinical chemistry, or urinalysis) or other safety assessments (eg, ECG, radiological scans, vital signs measurements), including those that worsen from baseline, considered clinically significant in the medical and scientific judgment of the investigator (ie, not related to progression of underlying disease).
- Exacerbation of a chronic or intermittent pre-existing condition including either an increase in frequency and/or intensity of the condition.
- New conditions detected or diagnosed after study treatment administration even though it may have been present before the start of the study.
- Signs, symptoms, or the clinical sequelae of a suspected drug-drug interaction.
- Signs, symptoms, or the clinical sequelae of a suspected overdose of either study treatment or a concomitant medication. Overdose per se will not be reported as an AE/SAE unless it is an intentional overdose taken with possible suicidal/self-harming intent. Such overdoses should be reported regardless of sequelae.
- "Lack of efficacy" or "failure of expected pharmacological action" per se will not be reported as an AE or SAE. Such instances will be captured in the efficacy assessments. However, the signs, symptoms, and/or clinical sequelae resulting from lack of efficacy will be reported as AE or SAE if they fulfill the definition of an AE or SAE.
- The signs, symptoms, and/or clinical sequelae resulting from lack of efficacy will be reported as AE or SAE if they fulfill the definition of an AE or SAE. Also, "lack of efficacy" or "failure of expected pharmacological action" constitutes an AE or SAE.

Events NOT Meeting the AE Definition

- Any clinically significant abnormal laboratory findings or other abnormal safety assessments which are associated with the underlying disease, unless judged by the investigator to be more severe than expected for the participant's condition.
- The disease/disorder being studied or expected progression, signs, or symptoms of the disease/disorder being studied, unless more severe than expected for the participant's condition.
- Medical or surgical procedure (eg, endoscopy, appendectomy): the condition that leads to the procedure is the AE.
- Situations in which an untoward medical occurrence did not occur (social and/or convenience admission to a hospital).
- Anticipated day-to-day fluctuations of pre-existing disease(s) or condition(s) present or detected at the start of the study that do not worsen.

Reporting of SAE to GSK**SAE Reporting to GSK via Electronic Data Collection Tool**

- The primary mechanism for reporting SAE to GSK will be the electronic data collection tool.
- If the electronic system is unavailable, then the site will use the paper SAE data collection tool (see next section) in order to report the event within 24 hours.
- The site will enter the SAE data into the electronic system as soon as it becomes available.
- The investigator or medically-qualified sub-investigator must show evidence within the eCRF (e.g., check review box, signature, etc.) of review and verification of the relationship of each SAE to IP/study participation (causality) within 72 hours of SAE entry into the eCRF.
- After the study is completed at a given site, the electronic data collection tool will be taken off-line to prevent the entry of new data or changes to existing data.
- If a site receives a report of a new SAE from a study participant or receives updated data on a previously reported SAE after the electronic data collection tool has been taken off-line, then the site can report this information on a paper SAE form (see next section) or to the medical monitor/SAE coordinator by telephone.
- Contacts for SAE reporting can be found at the beginning of this protocol on the Medical Monitor Contact Information page.

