9.3. Adverse Events

- The definitions of an AE or SAE can be found in Section [12.3 \(Appendix 3\)](#).
- The investigator and any designees are responsible for detecting, documenting, and reporting events that meet the definition of an AE or SAE and remain responsible for following up AEs that are serious, considered related to the study treatment or the study, or that caused the participant to discontinue the study treatment (see Section [8](#)).

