10.2. Sample Size Determination

10.2.1. Sample Size Assumptions

The sample size of this study has been primarily determined in order to achieve sufficient power for the principal secondary endpoint SF-36 vitality sub-score, since the anticipated effect size of this endpoint is less than that for the primary endpoint.

Approximately 600 participants are planned to be randomized (300 per arm) to receive daprodustat or placebo, who will be treated to achieve and maintain Hgb between 11 and 12 g/dL. Under the assumption that up to 10% of participants will withdraw from the study before Week 24 (start of EP), 600 randomized participants will result in at least 540 evaluable participants.

For the primary endpoint, the expected difference in mean Hgb change from baseline and the EP, between arms, is 1.0 g/dL and the anticipated between participant standard deviation (SD) is 1.5 g/dL, based on historical rhEPO trials and daprodustat clinical trial experience to date. The planned study size provides more than 99% power for superiority. In addition, it is anticipated that the smallest difference in mean Hgb change between arms that would meet the statistical criterion for superiority would be 0.25 g/dL.

For the first principal secondary endpoint of % of participants having a Hgb increase of ≥ 1.0 g/dL from baseline to EP, 540 evaluable participants provides $>90\%$ power to detect a 20% difference between daprodustat and placebo, assuming 30% of placebo arm participants will have a Hgb increase of ≥ 1.0 g/dL. In that case the smallest difference between daprodustat and placebo that would meet the statistical criterion for superiority would be 8%.

For the second principal secondary endpoint of mean change in SF-36 vitality sub-score between baseline and week 28, 540 evaluable participants provides for 79% power to detect a difference between arms under the assumption of a between treatment effect of 5 points in favor of daprodustat and a within-group standard deviation of 21 points. Prior research has determined that anemia is associated with a difference of 5.4 points from baseline for SF-36 vitality scores (Bjorner, 2007). It is expected that the smallest difference between arms that would meet the statistical criterion for superiority in this principal secondary endpoint is 3.5 points.

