8.2. Adverse Events Analyses

Adverse events analyses including the analysis of AEs of special interest (AESI), adverse events (AEs), Serious (SAEs) and other significant AEs will be based on GSK Core Data Standards. Adverse events will be coded using the Medical Dictionary for Regulatory Activities (MedDRA) coding dictionary. See Section [10.4.2](#) for AE treatment state definitions.

The analyses of the CEC-adjudicated MACE have been described in Section [8.1](#). However, AE summaries will also include the AEs and SAEs associated with the adjudicated events listed below:

CONFIDENTIAL

205270

- All-cause mortality (CV and non-CV mortality)
- Non-fatal MI
- Non-fatal stroke

For the purpose of AE summaries, the investigator-reported AE details will be used, regardless of the adjudication outcome of the event, unless otherwise specified.

AESIs

Adverse events of special interest and exposure-adjusted AE incidence rate calculation are described in Section [10.6.4](#).

Summaries of AESIs will include the number, percentage, and exposure-adjusted AE incidence rate per 100 person-years of subjects having at least one occurrence, the number of events, the number of subjects by number of occurrences, the characteristics of the AE (serious, drug-related, etc.), outcome, maximum intensity, time to first onset/worsening, and action taken summarized by treatment group. For each count, a subject will be summarized as follows:

- Serious/drug-related/severe/fatal: If any specific AE falls in the respective category, the participant will be counted in that category.
- Outcome: The participant will be counted within a category if there is at least one specific AE in that category.
- Maximum intensity: The specific AE with the maximum intensity will be counted for this purpose. For example, a participant will be counted in the ‘severe’ category if there is at least one specific AE with severe intensity. A participant will be counted in the ‘moderate’ category if there is at least one specific AE with moderate intensity and there is no specific AE with severe intensity.
- Time to first onset/worsening (days): The earliest of onset dates for the specific AE – treatment start + 1

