If the AE onset date/AE worsening and/or resolution date is missing or incomplete in the database for any occurrence of the specific AE, time to first onset/worsening and/or duration of the first, second, and third occurrence will be left missing for the participant. These summaries of special interest AEs will be provided for those AEs classified as treatment emergent.

Adverse Events

The number, percentage, and exposure-adjusted AE incidence rate per 100 person-years of participants reporting at least one AE will be provided for each treatment group. These events will be summarized by treatment group, primary system organ class, and preferred term. Similarly, the number and percentage of participants reporting at least one follow-up AE will be summarized by treatment group, primary system organ class, and preferred term.

In addition, all treatment emergent AEs will be summarized by treatment group, primary system organ class, higher level term and preferred term. In addition to generating number and percentage of subjects with treatment emergent SAEs, relative risk and 95% Wald confidence intervals will be presented for each HLT and PT as described in Section [10.6.4](#).

Summaries of all treatment emergent AEs will be produced for the following subgroups - age group, gender, race group, and weight quartile- by treatment group, primary system organ class, and preferred term.

A listing of AE records for all participants who reported AEs will be produced.

The number and percentage of participants reporting the most common treatment emergent AEs (those occurring in $\geq 5\%$ of participants in any treatment group) will be summarized by preferred term and treatment group.

The number and percentage of participants reporting treatment emergent AEs assessed by the investigator to be related to the study drug (termed as drug-related hereafter) will be summarized by treatment group, primary system organ class, and preferred term.

The number and percentage of participants reporting treatment emergent AEs by maximum intensity will be summarized by treatment group, primary system organ class, and preferred term.

The number and percentage of participants reporting treatment emergent drug-related AEs by maximum intensity will be summarized by treatment group, primary system organ class, and preferred term.

A listing of which participants reported specific adverse events will be produced.

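### Two adjacent bullets in Protocol Appendix 3 contradict each other on whether lack of efficacy is itself an adverse event, and the SAP does not say how such reports would be handled

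*Protocol*

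**What the plan says.** Protocol Section 9.3 gives no definition of its own and defers to the appendix: "The definitions of an AE or SAE can be found in Section" 12.3.

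In Section 12.3 (Appendix 3), under the events that meet the AE definition, two consecutive bullets deal with lack of efficacy.

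- **First bullet.** Lack of efficacy, or failure of the expected pharmacological action, "per se will not be reported as an AE or SAE. Such instances will be captured in the efficacy assessments". Signs, symptoms and clinical sequelae are handled differently: those "resulting from lack of efficacy will be reported as AE or SAE if they fulfill the definition of an AE or SAE".
- **Second bullet.** It repeats the rule on signs, symptoms and sequelae. It then adds that lack of efficacy or "failure of expected pharmacological action' constitutes an AE or SAE".

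The list of events that do not meet the definition excludes "The disease/disorder being studied or expected progression, signs, or symptoms of the disease/disorder being studied, unless more severe than expected" for the participant's condition. It does not mention lack of efficacy.

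SAP Section 8.2 sets the data source: "For the purpose of AE summaries, the investigator-reported AE details will be used", regardless of how an event was adjudicated and unless otherwise specified. For treatment-emergent events, "relative risk and 95% Wald confidence intervals will be presented for each HLT and PT". The same section plans tables of drug-related AEs, of AEs reaching 5% in either arm, and of AEs leading to discontinuation of randomized treatment.

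**The concern.** An investigator whose participant fails to respond has two instructions in force, one to record nothing as an AE and one to record the non-response as an AE. Sites that settle this differently will produce AE data that are not comparable with each other.

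The arms could also be affected unequally. The trial is designed on the expectation that fewer placebo participants will reach the target Hgb rise. If inadequate response is recorded as an AE, it will be recorded more often on placebo. That would move the AE comparison in favor of daprodustat for a reason that belongs to efficacy. Blinding does not prevent this, because sites measure HemoCue Hgb and apply the rescue criteria to it. They can see an inadequate response without knowing the arm.

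**Working it through.** The documents state no figure for this point, so there is none to reproduce. The check is a comparison of text, followed by an illustration of direction and scale.

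**Step 1. Do the bullets conflict?** Each has a part about sequelae and a part about the event itself. The parts about sequelae agree. On the event itself, the first bullet says not to report it and the second says it is an AE or SAE. This is a direct contradiction.

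**Step 2. Does other text settle it?**

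- Section 9.3 only points to the appendix.
- The exclusion of the disease under study, and the matching test for laboratory findings in Section 9.5.5, both turn on severity relative to expectation. Neither says which bullet governs.
- Sections 7.4 and 8.1 say how lack of efficacy or inadequate Hgb response is to be managed. They do not say whether it is reported as an AE.
- The SAP states no rule for lack-of-efficacy terms.

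**Step 3. Which tables would be affected?** The any-AE total, the drug-related tables, and the rows and relative risks for the term itself. The table of AEs leading to discontinuation may also be affected: Section 8.1 requires permanent discontinuation when rescue criteria are met, and an investigator could attach a lack-of-efficacy AE to that decision.

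**Step 4. Direction and scale (illustration only).**

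Inputs from Protocol Section 10.2.1:

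- The response endpoint (Hgb rise of at least 1.0 g/dL) is powered for "a 20% difference between daprodustat and placebo, assuming 30% of placebo arm participants" respond. Planned response is therefore 30% on placebo and 30% + 20% = 50% on daprodustat.
- Non-response is 100% − 30% = 70% on placebo and 100% − 50% = 50% on daprodustat. It serves here as a proxy for lack of efficacy.
- Planned randomization is 300 per arm, taken as the approximate size of the Safety population.

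Assumption: a share f of non-responders is recorded as an AE, the same in both arms. The documents give no value for f, so a range is shown.

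Placebo excess for the term = f × (70 − 50) = 20 × f percentage points.

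| f | Placebo | Daprodustat | Excess | Extra placebo participants (of 300) |
|---|---|---|---|---|
| 0 (first bullet followed) | 0% | 0% | 0 | 0 |
| 5% | 3.5% | 2.5% | 1 point | 3 |
| 20% | 14% | 10% | 4 points | 12 |
| 100% (ceiling) | 70% | 50% | 20 points | 60 |

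The relative risk for the term is (0.50 × f)/(0.70 × f) = 0.71 at any f above zero. The term would reach the 5% common-AE table once 0.70 × f ≥ 0.05, that is f ≥ 7.1%.

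**Step 5. Effect on overall AE incidence.** A participant who already has another AE adds nothing to the any-AE percentage. If a share q of those with the term has another AE, equal in both arms, the excess falls to 20 × f × (1 − q) points. It lies between zero (q = 1) and the figures in the table (q = 0).

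**The case against.** The strongest case on the other side accepts the contradiction and disputes its consequence.

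- **Other rules hold reporting back.** The disease-under-study exclusion and the laboratory rule in Section 9.5.5 discourage recording bare non-response. Sections 7.4 and 8.1 direct investigators to rescue therapy or the dosing algorithm. This stands as a limit on f. A reader might infer that every inadequate Hgb response would be reported, and these sections do not support that. They also do not cancel the second bullet.
- **The effect would be visible.** AEs are tabulated by preferred term, so lack-of-efficacy terms would have their own rows. AESIs are found through predefined term lists (SAP Section 10.6.4), and MACE is adjudicated under blind. The protocol plans descriptive safety summaries, and no AE comparison is in the testing hierarchy. This stands too. It confines most of the distortion to the totals and tables named in step 3, and does not remove it from them.
- **Placebo participants may do well.** Protocol Section 5.4 expects few drop-outs for lack of effect and notes that such patients can maintain or raise their Hgb. That argues against reading lack of efficacy as far more common on placebo. The planning ratio is 70 to 50, or 1.4 to 1.

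A reader might also infer that placebo SAE incidence would rise, since the second bullet names SAEs. Section 12.3.1 requires a seriousness criterion, and failure to raise Hgb does not meet one by itself. A case that did would usually be a clinical sequela, which both bullets already make reportable.

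**Conclusion.** The contradiction is certain. It sits in the definition that governs AE reporting, and neither document resolves it. The possibility of inconsistent reporting between sites follows directly and needs no numerical assumption.

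The size of any effect on the AE comparison is unknown. The direction, more on placebo, rests on the planning response rates, on Hgb non-response as a proxy for lack of efficacy, and on equal reporting in the two arms. Under those assumptions the excess for the term is 1 point at f = 5% and 4 points at f = 20%, and less for overall AE incidence. Counts would rise in both arms, only more on placebo. The documents do not support a claim that the safety conclusions are materially biased. The primary and principal secondary endpoints are unaffected. This is an internal inconsistency that should be corrected.

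**What to change.** 1. **Protocol Appendix 3:** delete the second bullet. Apart from its contradictory last sentence it only repeats the first, so deletion leaves one rule: lack of efficacy is captured as efficacy, and its signs, symptoms and sequelae are reported if they meet the AE definition.
2. **Sites:** send a short letter stating that rule.
3. **SAP Section 8.2, before unblinding:** state that AE terms recording only lack of efficacy will be identified under blind and shown separately, and that the AE totals will also be given without them. This covers reports already made. The identification can be done at the data review that SAP Section 4.1 already schedules before unblinding.

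The cost is a one-bullet protocol clarification, a site letter, a short SAP addition and one repeat of the AE totals. No new data are needed.
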